2 LIST OF ABBREVIATIONS

3D	3 Dimensional
AE	Adverse events
BED	Biologically Equivalent Dose
CBCT	Cone Beam Computed Tomography
CPC	Cancer Protocol Committee
CT	Computed Tomography
CTCAE	Common Terminology Criteria for Adverse Events
CTV	Clinical Tumor Volume
DCI	Duke Cancer Institute
DLT	Dose Limiting Toxicity
Dmax	Maximum dose to any voxel within a volume
DUHS	Duke University Health System
G3 or G4	Grade 3 or Grade 4 toxicity
GCP	Good Clinical Practice
GTV	Gross Tumor Volume
GY	Gray
HDR	High Dose Rate
HVLT	Hopkins Verbal Learning Test
ICRU	International Commission on Radiation Units and Measurement
ID	Identification
IMRT	Intensity Modulated Radiation Therapy (including Volumetric Modulated Arc Therapy)
IRB	Institutional Review Board
KPS	Karnofsky Performance Scale
LINAC	Linear Accelerator
LRC	Loco-regional control
MMSE	Mini-Mental Status Examination
MRI	Magnetic Resonance Imaging.
MTD	Maximum Tolerated Dose
MV	Megavoltage
NCI	National Cancer Institute
OS	Overall Survival
PET	Positron Emission Tomography
PI	Primary Investigator
PTV	Planning Target Volume
RTOG	Radiation Therapy Oncology Group
SIMT	Single Isocenter Multi-Target
SOC	Safety Oversight Committee
SRS	Stereotactic Radiosurgery
TD5/5	Toxic dose of 5% at 5 years
V ₁₂	Volume of normal brain receiving 12 Gy
VMAT	Volumetric modulated arc therapy
WBRT	Whole Brain Radiation Therapy

3 PROTOCOL SYNOPSIS AND RESEARCH SUMMARY

3.1 Purpose

To examine the effectiveness and efficiency of Single Isocenter Multi-Target Stereotactic Radiosurgery (SIMT SRS) in patients with four or more brain metastases.

Primary Objective

1. Assess the impact of using linear-accelerator-based, single-isocenter, image-guided stereotactic radiosurgery on the survival of patients with four or more brain metastases.

Secondary Objectives

1. Describe the time to local brain recurrence
2. Describe the time to distant brain recurrence
3. Describe the time to death due to neurologic causes
4. Describe the prevalence of significant adverse events

Exploratory Objectives

1. Describe changes over time in neurocognition
2. Describe changes over time in quality of life
3. Quantify treatment set-up and dosimetric data for this treatment technique
4. Describe the rate of salvage therapy
5. Describe prevalence of radionecrosis at the SRS site
6. Describe length and intensity of steroid usage post-SRS

Hypotheses

1. This protocol will test the hypothesis that SIMT SRS in patients with four or more brain metastases is efficacious and can be delivered efficiently with minimal toxicity and no significant effect on quality of life and neurocognition.

3.2 Background and Significance

Brain metastases (BM) occur in 10 - 40% of cancer patients^{1,2} with variable incidences according to the primary disease. Despite advances in diagnosis and treatment, the development of brain metastases is typically associated with short life expectancy. For patients with a limited number of BM, surgery and whole brain radiotherapy (WBRT) may improve local control and survival.^{3,4} However, WBRT is associated with neurocognitive deficits without offering a survival advantage over a more focal radiotherapy approach such as stereotactic radiosurgery (SRS).⁵⁻⁸ The use of SRS alone provides a very high response rate and local control.^{6,9,10}

SRS treatment is usually recommended for a limited number of BMs, mostly for 1-3 lesions.^{8,11} However, with evolving radiotherapy technology and brain imaging and recognition of the WBRT long-term side effects, there is a growing interest in using SRS treatments for patients with more than a limited number of BM. A prospective trial looking into SRS, without WBRT, for patients with up to 10 brain metastases found no survival or local recurrence difference between patients treated for 2-4 BMs and those with 5-10 BMs.¹² In fact, cumulative tumor volume and largest treated tumor size were more significant predictors of outcome than the number of treated lesions.

Another obstacle in using SRS for the treatment of a larger number of BMs is the lengthy treatment time required when each lesion was treated with a separate stereotactic radiotherapy plan. SIMT volumetric modulated arc therapy (VMAT) for SRS planning and delivery enables the treatment of many lesions simultaneously. This technique was shown to substantially reduce treatment time with the potential for small improvements in conformity indexes and normal brain dose compared with multiple isocenter plans.^{13,14} Data on clinical outcomes with the use of this technique is sparse with one study showing high local control and a survival rate of 60% after 6 months.¹⁵

The 2016 NCCN guidelines for treating patients with >3 brain metastases recommends WBRT or SRS based on the treating physicians' clinical assessment and judgment. Choosing the most appropriate patients with multiple BMs for SRS treatment rather than WBRT remains an unresolved issue. The goal of this study is to evaluate the efficacy and safety of SIMT SRS as well as the impact of this technology on neurocognition and quality of life.

3.3 Design and Procedure

Forty patients with four or more brain metastases will be enrolled prior to radiosurgery. A planning MRI brain scan will be performed with GD-DPTA within one week prior to radiosurgery, per the standard of care. Patients who have completed a diagnostic MRI with contrast within 14 days of radiosurgery do not need to have a planning MRI. At that time, Neurocognitive (Mini-Mental Status Examination (MMSE), Trail-making test A&B, Hopkins Learning Verbal (HVL)) and functional assessment of cancer therapy-brain (FACT- Br) will also be obtained. Dose will be prescribed to the maximum isodose line encompassing the resulting PTV using the dose guidelines as described below.

The primary endpoint will be the proportion of patients who live longer than predicted based on the diagnosis-specific GPA score. The Kaplan-Meier estimator will be used to describe the survival of all patients treated with SIMT SRS. Secondary endpoints will be the rate of recurrence at the treated metastases sites, the rate of new brain metastases at a site different from the SRS-treated metastases sites, the rate of death due to neurological causes, and the prevalence of significant adverse events. Exploratory endpoints include change over time in neurocognition and quality of life, quantification of dosimetric measures, the rate of salvage therapy, the rate of radionecrosis at the SRS treatment sites, and the rate and intensity of steroid-usage post-SRS. Dosimetric endpoints to be collected include: maximum and minimum dose to GTV, and conformity index. These endpoints will be compared to historical data calculated by Sperduto et al. from the literature on radiosurgery alone, radiosurgery plus WBRT or WBRT alone, where appropriate.¹⁶ All patients will be evaluated for neurocognitive function via MMSE, HVL, and Trail-making tests A & B, quality of life via FACT-Br, and for local recurrence via MRI every 3 months over the course of the study. These evaluations will be done at regular follow-up evaluations or when local recurrence is suspected on the basis of symptoms. Distant recurrence is defined as the appearance of new brain metastases at a site different from that of the original metastases. Recurrence will further be defined as a new area of enhancement that measures greater than 5 millimeters in the axial plane on MRI. The length of time to recurrence of the original brain metastases will be calculated from the date of the brain metastases radiosurgery to the date that a recurrence was detected by MRI. Patients with suspected recurrent tumor and/or who are symptomatic may undergo a stereotactic biopsy to evaluate for radionecrosis versus recurrent brain metastases, as is standard of care.

There may or may not be a direct medical benefit to participants. The hope is that but the information gained from this study will help in treating patients with brain metastases in the future.

3.4 Selection of Subjects

Inclusion criteria:

1. A contrast-enhanced MRI scan showing ≥ 4 treatable brain metastases.
2. Age ≥ 18 years of age.
3. KPS ≥ 70
4. Patient must have a GPA score 0.5 or greater (See Appendix A)
5. Life expectancy of at least 3 months
6. Postoperative patients with resected brain metastases are eligible.
7. Largest lesion ≤ 4 cm diameter
8. Must be a candidate for MRI imaging
9. Previous cranial SRS/WBRT is allowed if > 3 months prior to SIMT
10. Must be capable of providing informed consent.
11. Women of childbearing age must have a negative serum pregnancy test to meet eligibility per Duke Policy. Adequate birth control must be used if childbearing potential as outlined in the protocol.

Exclusion

1. Primary lesion with the following histologies: small cell carcinoma, germ-cell tumors, lymphoma, leukemia, and multiple myeloma.
2. Metastases within 2 mm of the optic apparatus
3. Patients unable to obtain MRI.
4. Evidence of leptomeningeal disease
5. Greater than 10 brain metastases; excluding previously treated and stable brain metastases.
6. Pregnant women are excluded.

3.5 Duration of study

The study will last three years. We aim to accrue 40 patients. Overall survival, local control, distant failure, neurocognition, and quality of life will be collected on the 3, 6, 9, and 12-month time points.

3.6 Data Analysis and Statistical Considerations

Though local control is of primary interest in this study, there is concern about the ability to differentiate between swelling due to radiation and disease progression without conducting a biopsy. The use of a biopsy to determine recurrence is not feasible given the number of brain metastases. Hence we focus on the survival of patients newly diagnosed with brain metastases who are treated with SIMT SRS. The goal of the study is to confirm that use of SIMT SRS does not reduce the prognosis of patients.

The population of patients newly diagnosed with brain metastases is a heterogeneous population with expected survival ranging between 3 and 25 months. We will use the expected survival defined by the diagnosis-specific GPA (Graded Prognostic Assessment) index to assess the efficacy of SIMT SRS.¹⁶ Specifically, for each patient we will determine whether the patient lives longer than expected based upon the GPA index. If the survival of patients treated with SIMT SRS is truly comparable to the survival of patients treated with currently available treatment regimens, then we would expect that approximately half of the patients would live longer than expected. A test of non-inferiority will be conducted to assess whether the survival of patients treated with SIMT SRS is similar or better than that seen among Sperduto's cohort.¹⁶ Factors such as the technical feasibility of administering SIMT

SRS and clinical factors such as neurologic control and local control will be considered in determining whether further usage of SIMT SRS is reasonable.

Additionally, the Kaplan-Meier estimator will be used to describe the survival of all patients treated with SIMT SRS. The survival of patients within diagnosis-specific subgroups will also be similarly described. Within the context of the Kaplan-Meier estimator, median survival, 6-month survival, and 12-month survival will be estimated. Survival is defined as the time between initiation of SIMT SRS and death, and will be censored at last follow-up if the patient remains alive.

4 INTRODUCTION

4.1 Study Disease

While systemic therapy has improved for many cancers including melanoma, breast, NSCLC, GI, and renal cell carcinoma, the blood brain barrier prevents many of these agents from being effective in the brain. Thus as systemic therapies have increased survival, brain metastases have become more prevalent. The consequences of brain disease are devastating with complications ranging from headache and seizures to paralysis, so maximizing control while minimizing side effects is crucial. The historical standard of care has been whole brain radiation therapy, which can be effective in controlling some tumors but patients will inevitably experience neurocognitive decline as a side effect of this therapy.

4.2 Radiation Therapy

Stereotactic radiosurgery (SRS) has emerged as standard of care treatment for those patients with 1-3 brain metastases. This treatment has surpassed whole brain radiation therapy with regard to superior local control of brain metastases as well as preservation of neurocognition and quality of life.⁸ Now that new systemic therapies are increasing life expectancy, in patients who have brain metastases it is imperative to preserve neurocognition while managing local control.

With advances in radiosurgery technology, it has become possible to stereotactically treat multiple targets at once in an efficient and accurate manner rather than treating each metastasis with SRS individually which would be time consuming and difficult for the immobilized patient. There have been at least three single institutional studies that examine the feasibility of SIMT SRS but do not report clinical outcome.^{13,14,17} There has been one small study of 26 patients with a range of 2-13 metastases which reported clinical outcome but did not study quality of life and cognitive endpoints. One year local control was reported to be 83%, but median follow up for all patients was only 3.3 months.¹⁵

[figure not shown]
4.3 Study Purpose/Rationale

There has not been a prospective trial investigating efficacy, survival and quality of life endpoints. The purpose of this study is to demonstrate the efficacy and efficiency of SIMT technology for the simultaneous treatment of multiple brain metastases, as well as to evaluate quality of life and cognition endpoints. We are already using SIMT technology in our clinic as our current departmental standard of care for patients with multiple (≥ 4) brain metastases and have seen excellent results in terms of local control and quality of life. We are currently working on publishing our retrospective results and there is a need for a prospective trial demonstrating the efficacy of this technology.

5 OBJECTIVES AND ENDPOINTS

	Objective	Endpoint	Analysis
Primary	Assess the impact of using SIMT SRS for the treatment of brain metastases on survival	Proportion of patients who live longer than predicted according to the Graded Prognostic Assessment (GPA) score	See Section 13.4
Key Secondary	Describe the time to local brain recurrence	Proportion of patients that experience local brain recurrence within 1 year of SIMT SRS treatment.	See Section 13.5.1
Other Secondary	Describe the time to distant brain recurrence	Proportion of patients that experience a new brain metastasis at a site different from the original brain metastasis site 1 year after SIMT SRS treatment	See Section 13.5.2
Other Secondary	Describe the time to death due to neurological causes	Proportion of patients who are dead within 1 year of SIMT SRS treatment due to neurologic reasons	See Section 13.5.2
Other Secondary	Describe the prevalence of significant adverse events	Proportion of patients who experience grade 3, 4, or 5 neurologic adverse events attributable to SIMT SRS	See Section 13.5.2
Key Exploratory	Describe changes over time in neurocognition	Mean changes from baseline in subscales of the Trailmaking instruments and the HLVT	See Section 13.6.1
Key Exploratory	Describe changes over time in quality of life	Mean changes from baseline in subscales of the FACT-Brain instrument	See Section 13.6.1
Other Exploratory	Quantify treatment set up and dosimetric data for this treatment technique	Mean length of time to set-up and treat patient, Volume of brain exposed to 12Gy, Mean PTV dose, Total volume of all brain metastases, conformity index, maximum dose	See Section 13.6.2
Other Exploratory	Describe the rate of salvage therapy	The proportion of patients who receive salvage treatment after failing SIMT SRS	See Section 13.6.2
Other Exploratory	Describe prevalence of radionecrosis at the SRS site	Proportion of patients with radionecrosis at the SRS site; the proportion of lesions showing radionecrosis	See Section 13.6.2
Other Exploratory	Describe length and intensity of steroid usage post-SRS	Descriptive statistics	See Section 13.6.2

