8.1.2 Safety Considerations

Patients will be evaluated throughout the study for toxicity. Patients will be assessed for all adverse events during treatment and post completion of SRS. Adverse events will be considered to be any grade 3, 4, or 5 event that is deemed by the PI to be probably, possibly, or definitely related to the SRS treatment. Acute adverse events will be collected at the first post-SRS visit. This visit will occur approximately 4 weeks after the last fraction of SRS is

delivered. These will be collected and reported. In our experience, SRS treatment side effects are rare and are solely neurologic.

In light of previous observations, it may be that increasing the treatment volume may also come with a potential cost of increased morbidity.

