11.1.1 AEs of Special Interest

Patients will be evaluated throughout the study for toxicity. Patients will be assessed for all adverse events during treatment and post completion of RT. Adverse Events (AEs) that are deemed by the PI to be related to the SIMT SRS treatment will be collected and reported. Acute adverse events will be collected at the first post-SRS visit. This visit will occur approximately 4 weeks after the last fraction of SRS is delivered. While not all-inclusive, the list below indicates side effects that may be related to the treatment. In the largest trial examining SRS treatment to 5-10 multiple targets (n = 1194), grade I & 2 toxicity was seen in 5% and Grades 3-4 were seen in 3%, and grade 5 toxicity <1%.¹²

SRS Possible Side Effects

Likely:

Mild erythema in the treatment field
Nausea / vomiting
Headaches
Fatigue

Less likely:

Hair loss in the treatment field
Decreased mental abilities
Extremity weakness
Parathesias
Speech difficulties
Hydrocephalus
Radionecrosis
Seizures
Vision loss
Death

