13.5.2 Other Secondary Objectives

The time until distant brain recurrence will be calculated as the time between initiation of SIMT SRS and distant recurrence of brain metastases. The time to distant brain recurrence will be censored at the time of last follow-up if the patient remains alive without distant recurrence, or will be censored at death if the patient dies without distant recurrence of brain metastases. A Kaplan-Meier estimator will be used to describe the time until distant recurrence. An estimate of the proportion of patients without distance recurrence one year after SIMT SRS treatment will be generated. The time until distant brain recurrence will also be described within diagnosis-specific subgroups.

Time to neurologic death is defined as the time between initiation of SIMT SRS and death due to neurologic causes. If a patient remains alive or dies for reasons unrelated to neurologic disease, the time to neurologic death will be censored at the time of last follow-up or death not due to neurologic causes. Analyses similar to other “time to an event” outcomes will be conducted including the generation of Kaplan-Meier curves.

The proportion of patients who experience grade 3 or worse neurologic toxicity attributable to SIMT SRS will be summarized. In addition, adverse events experienced by protocol subjects will also be summarized in several other forms to satisfy scientific and monitoring needs, as well as various regulatory reporting needs (e.g. DCI SOC, and ClinicalTrials.gov). The frequency of adverse events that are possibly, probably, or definitely related to protocol treatment will be tabulated by the maximum grade for each type of adverse event.

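### The only patient-level grade 3-5 toxicity proportion defined as an endpoint counts neurologic events alone, so it is narrower than its objective and can understate significant related toxicity

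*Combined protocol and SAP*

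**What the plan says.** **Objective.** Section 3.1 lists as a secondary objective: "Describe the prevalence of significant adverse events". The synopsis (3.3) names the matching endpoint in the same general terms, without restriction to an organ system.

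**Endpoint and analysis.** In the section 5 table the endpoint is "Proportion of patients who experience grade 3, 4, or 5 neurologic adverse events attributable to SIMT SRS". Section 13.5.2 agrees: "The proportion of patients who experience grade 3 or worse neurologic toxicity attributable to SIMT SRS will be summarized". That section goes on to promise further adverse event summaries for scientific, monitoring and regulatory purposes. It also promises a table of all possibly, probably or definitely related events by maximum grade within each event type.

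**Safety text.** Section 8.1.2 is broader: "Adverse events will be considered to be any grade 3, 4, or 5 event that is deemed by the PI" to be possibly, probably or definitely related to SRS. The same section then remarks: "In our experience, SRS treatment side effects are rare and are solely neurologic". Section 11.1.1 lists possible side effects. Among them are "Mild erythema in the treatment field", "Nausea / vomiting" and "Hair loss in the treatment field".

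**Collection.** Section 11.1 requires every event judged related to SIMT treatment to be recorded, whatever its type.

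**The concern.** The objective is general and the endpoint that serves it is a subset. A proportion based on a subset of events can only equal or fall below the proportion based on all of them, so any discrepancy is in the favourable direction. The study hypothesis in 3.1 includes a claim of minimal toxicity, and readers will look to this proportion for support.

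Two features of the text make this more than a matter of labels. First, no section defines neurologic or says who classifies an event. Related severe vomiting, vision loss or death could be counted or not by a judgement made after the event is known. Second, the remark in 8.1.2 that would make the restriction harmless conflicts with the list in 11.1.1, where erythema and hair loss are plainly not neurologic and nausea, vomiting and fatigue are not clearly so.

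**Working it through.** The plan gives no target, threshold or precision for the toxicity endpoint, so there is no stated figure to reproduce. The check is a comparison of the text, followed by a calculation for scale.

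**1. Which events count, section by section**

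| Section | Scope |
|---|---|
| 3.1 and 3.3 | significant adverse events, no organ limit |
| 8.1.2 | any related grade 3-5 event |
| 5 and 13.5.2 (proportion) | related grade 3-5 neurologic events only |
| 13.5.2 (table) | all related events, by type and maximum grade |

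Sections 5 and 13.5.2 agree with each other. Both are narrower than 3.1, 3.3 and 8.1.2.

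**2. Can the by-type table supply the missing proportion?** No. A patient with two severe events of different types appears in two rows. Suppose one row shows one patient at grade 3 and another row also shows one. The number of patients affected is then either 1 or 2, so the any-type proportion is 1/40 = 2.5% or 2/40 = 5.0%. The table gives bounds, not the proportion.

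**3. Scale**

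Inputs:
- n = 40 (13.8).
- Background toxicity from the cited multi-target SRS study (11.1.1): grade 3-4 in 3%, grade 5 in under 1%. The total T is therefore taken as 3% to 4%. I assume these are per-patient rates for all event types; 11.1.1 does not say they are neurologic only.
- Non-neurologic share s of patients with a severe related event. The documents do not give it, so it is assumed to lie between 0% and 50%.

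Expected patients with any grade 3-5 event: 40 × 0.03 = 1.2 to 40 × 0.04 = 1.6. Chance of at least one: 1 − 0.97^40 = 70% to 1 − 0.96^40 = 80%.

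Shortfall = T × s. Expected uncounted patients = 40 × T × s. Chance of at least one uncounted = 1 − (1 − T × s)^40.

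| T | s | Counted rate T(1 − s) | Shortfall (points) | Expected uncounted | Chance of at least one uncounted |
|---|---|---|---|---|---|
| 3% | 0% | 3.0% | 0 | 0 | 0% |
| 3% | 25% | 2.25% | 0.75 | 0.3 | 26% |
| 3% | 50% | 1.5% | 1.5 | 0.6 | 45% |
| 4% | 0% | 4.0% | 0 | 0 | 0% |
| 4% | 25% | 3.0% | 1.0 | 0.4 | 33% |
| 4% | 50% | 2.0% | 2.0 | 0.8 | 55% |

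**4. Against sampling error.** One patient is 1/40 = 2.5 percentage points. Exact (Clopper-Pearson) 95% intervals are 0 to 8.8% for 0/40, 0.1% to 13.2% for 1/40 and 0.6% to 16.9% for 2/40. Leaving out one patient of two would move the estimate from 5.0% to 2.5%, with intervals that largely overlap.

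**The case against.** The strongest reply is that little would be hidden. Section 11.1 has every related event recorded, and section 13.5.2 tabulates all of them by type and grade, with other summaries promised. A related grade 3 vomiting event would be reported. The endpoint is stated consistently in 5 and 13.5.2, a focus on neurologic harm is natural for brain radiosurgery, and the non-inferiority rule in 13.8 uses survival only. All of this stands, and it limits the weight of the point. It does not supply the missing quantity: none of the named summaries is a proportion of patients with any related grade 3-5 event.

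A reader might infer more than the documents support in three ways:

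- *That the endpoint was restricted because of the remark in 8.1.2.* No section makes that link. The remark is about local experience, and the plan gives no reason for the restriction.
- *That this is the only patient-level toxicity figure.* It is not. Section 5 also has an exploratory proportion of patients with radionecrosis, and 13.6.2 summarises radionecrosis at patient level. It is, however, the only graded one.
- *That 11.1.1 shows severe non-neurologic events are expected.* The list carries no grades, describes the erythema as mild and is said not to be exhaustive. Most of the other entries are neurologic. It contradicts 8.1.2 on the type of side effect, not on severity.

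**Conclusion.** The point holds as a modest one. As written, the only patient-level grade 3-5 toxicity proportion defined as an endpoint can omit related severe events that the objective, the synopsis and 8.1.2 would include. The direction of any error is certain, because a subset cannot exceed the whole. Its likely size is small: 0 to 2 percentage points, or 0 to 0.8 expected patients in 40, well inside the width of the exact intervals. That range rests on carrying the 3-4% background rate over to this trial and on the assumed 0-50% non-neurologic share, for which the documents give no figure. Because the background rate is not described as neurologic only, setting the endpoint beside it may also compare unlike quantities. The change is worth making because it is cheap, not because a large bias has been shown.

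**What to change.** - In sections 5 and 13.5.2, add the proportion of treated patients with any grade 3, 4 or 5 event possibly, probably or definitely related to SIMT SRS, with an exact 95% confidence interval.
- Keep the neurologic proportion as a component of it. State in advance which events count as neurologic and who classifies them.
- Reconcile the remark in 8.1.2 on the type of side effects with the list in 11.1.1, and align the synopsis endpoint in 3.3 with section 5.

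The cost is wording and one extra line of output, since related events of every type are already recorded under 11.1. The only downside for the sponsor is that the reported toxicity rate may be slightly less favourable.
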